7.8. Intervention

The SAMSON (Safety and Adherence to Medications and Self-care advice in Oncology) intervention solution, is the next iteration of the REMIND intervention. REMIND was developed and assessed in 10 patients with CML. Results of the REMIND trial have been published:

Pilot Randomized Controlled Trial Study Protocol
Version 1.0 – 2 May 2023, Amendment 1 dated 26 June 2023

SAMSON is a digital support tool used in conjunction with usual care to improve adherence, reduce administration and interaction errors, and provide evidence-based advice for effective management of medication side-effects. It includes two elements:

- 1) SAMSON mobile app, including smartphone-based app to remotely prompt MA, monitor patient side-effects and deliver self-care advice; and computer-based app to enable adherence and side-effect reporting. The beta-version of SAMSON mobile app has been tested on 30 people with haematology cancer at Peter Mac in 2021 (HREC/74134/PMCC). Data on patient's diagnosis and treatment will be extracted from the patient's medical record at PeterMac. Data on drug administration, indications, cautions and side-effects, and counselling have been developed by Peter Mac Pharmacy Medicines Information Service, based on approved product and consumer information resources (Appendix 1). Self-care advice information has been developed based on resources such as American Society of Clinical Oncology (ASCO), Cancer Australia, Health Direct and Peter Mac's information for patients and carers, and reviewed by the SAMSON clinical team (Appendix 2). All data will be entered into the SAMSON platform by the RC. Drugs names and dosages will be matched with the patient's prescription; thus the patient will only receive prompted reminders and feedback on medication adherence status relating to their own treatment. Examples of how this information is shown in the SAMSON app are in Appendix 3. The project team member will debrief study nurses and pharmacists on how to use the SAMSON webpage at the beginning of the study, and continue providing IT support for them if issues arise.
- 2) Health professional tele-consultations, using MI skills being trained via the MITP to promote patient's adherence and side-effect self-management by:
 - Medication reconciliation,
 - MA education,
 - Medication administration, missed dose and side-effect education, including side-effect management strategies,
 - Assessment of barriers and concerns
 - Addressing barriers and concerns

MITP is a digital training platform, which was created to provide general training on MI, communication skills with focus on MA aspects for oncology clinicians. The MITP consists of different eLearning adaptive, interactive and possibly personalised modules, including formative assessments, being provided online via Peter Mac's learning management system (LMS) (Learning Hub). The MITP was developed in 2022 and is being trialled by oncology clinicians at Peter Mac. After the study's completion, expected in March 2023, the MITP will be refined accordingly, and will then be delivered in conjunction with the refined SAMSON mobile app as the SAMSON intervention solution in this study.

The structured counselling sessions will be either in person or online at baseline, week 1, 4, 8 and 12. The quantity and length of consultations will be tailored to patient's need and adherence status, assessed by the consultant. The initial consultation will be delivered in person or online by a pharmacist when patients receive their medicines. The tele-counselling sessions will be delivered via phone or telehealth by clinical nurses or pharmacists of participating departments at Peter Mac. In departments where there is no allocated clinical pharmacist, nurses will deliver teleconsultations or an alternative approach will be arranged in discussion between the patient's care team.

Nurses and pharmacists will participate in the study depending on their availability and interest. They will need to have at least one year of clinical experience in providing oncology care and successfully complete the MITP training to conduct the structured counseling sessions with participants. Study nurses and pharmacists will be provided instruction manuals to guide them for each consultation. It is predicted that some nurses and pharmacists involved in the MITP testing study in 2022 will

participate in the trial. The UTAUT questionnaire for healthcare professionals includes a statement that by completing the survey, they provide implied consent for the research team to use the data from this questionnaire for the purposes of the research project.

The online intervention manual (Attachments 4a and 4b), summarising details of the intervention, has been developed to guide the nurses and pharmacists while delivering the intervention. Besides this, they will be provided with the SAMSON website user manual (Attachment 3b). They will also work together to schedule who deliver which sessions. After each consultation, nurses/pharmacists will need to send to the RC a consultation checklist and summary, and concurrently send a consultation summary to the patient.

7.9. Procedure outlines

7.9.1. Patients randomised to the intervention arm

- At the initial pharmacist consult, participants will undergo an initial 30-60 minutes in person/online appointment with a SAMSON trained pharmacist, which will include a medication reconciliation and contra-indication assessment, MA, administration, missed dose and side-effect education, discussion about where on the APP side-effect solutions are located, an opportunity for the participant to discuss any concerns and ask questions. The pharmacist will record identified barriers and facilitators to MA in the SAMSON web-based system under the patient consultation notes section. These will be addressed in the following consultations.
- During the first week an intervention nurse/pharmacist will consult (either via phone or telehealth) the participant to commence the intervention. The tele-counselling session will be 15-30 minutes in duration (Appendix 10). Components of the teleconsultation session are outlined below.
 - Establishing the patient's understanding of the diagnosis, current symptom experience and medication regimen, and current self-care strategies.
 - Exploring any barriers to treatment adherence of the patient; particularly side-effects or other negative consequences.
 - Providing evidence-based self-care strategies
 - Exploring patient perceived benefits associated with MA.
 - Identifying the top concerns about MA (from the initial consultation notes) for each patient and address these concerns, using MI approach
 - Then, negotiating a plan of action based on discussions and arrange the next scheduled tele-consultation.
- Daily, a smartphone reminder message will be sent to the patient for each medication and dose based on their individual dosing regimen. The patient will be asked to respond to the message for each medication reminder by clicking the 'Yes' button to confirm they took the medication or the 'No' button if they did not take the medication on that occasion.
- Once a week, participants will be sent a message to their smartphone with a link to the weekly Side-Effects Survey that assesses the presence, severity and bother levels of common medication related side-effects. Participants will complete the survey via the app. The SAMSON system will record key medication-related toxicities and this information will be stored on a secure centrally-stored server to enable clinician review, and review weekly by the nurse/pharmacist conducting the tele-consultation. The SAMSON app provides evidence-based symptom self-care information to patients for each of the common toxicities, which is available to the patient in real-time. In addition, for severe or potentially life-threatening symptoms, e.g. fever, the app will notify the participant to seek immediate medical attention and generate an alert to be sent to the participants treating clinician and the study nurse.

Pilot Randomized Controlled Trial Study Protocol
Version 1.0 – 2 May 2023, Amendment 1 dated 26 June 2023

- The nurse/pharmacist will contact patients via phone/telehealth at an arranged time in weeks 4, 8 and 12 (Appendix 10). These consultations will take 15-30 minutes and be focused on any new issues with adherence or side-effects, as well as outstanding barriers to adherence and adherence levels that are suboptimal. The length of consultations will be tailored to patient's need and adherence status, assessed by the healthcare professional who delivers the counselling sessions. The consultation style will be one of guidance to assist the participant with development of their own strategies suitable to their lifestyle and values that enable optimisation of health behaviours. This is consistent with MI, an evidence-based method of modifying health behaviours.
- The SAMSON platform provides patient MA and side-effect reports to the treating clinician. Both the treating clinician and the patient can login to the SAMSON platform to view the patient's adherence and side-effect reports.
- At the beginning of the study, the patient will be educated that if they experience any severe or concerning symptoms, e.g. a fever equal to or above 38 degrees at any time during the 16-week intervention, they should report to the treating team by the preferred method (pager, email, phone) to alert them of this event as per standard processes, and the treating team will follow-up with the participant to ensure they received medical assistance. Symptoms reported via the SAMSON smartphone app will be actioned by the SAMSON team (clinical referral to medical/nursing as appropriate), however, this is secondary to standard care processes and referral pathways. Any urgent care enquires should follow standard care processes.
- We will 'buy out' nurses' and pharmacists' time to deliver MI consultations in the study.

7.9.2. Patients randomised to the controlled arm

- Participants in the control/usual care arm will receive usual care and will not have access to any of the intervention. Standard care will involve:
 - A consultation in the clinic with the clinic clinician, to provide education about medication, and patient-focused management of side-effects including the appropriate action to take regarding serious side-effects (e.g. when/where to seek urgent medical attention). The disease stream nurse will be the patient's ongoing contact for the management of any side-effects related to their treatment medication.
 - An initial pharmacist consultation at Peter Mac for the patient who chooses to fill their prescription at Peter Mac. In this consult, a medication reconciliation and medication dispensary consultation is conducted with a pharmacist to catalogue the patient's prescription and non-prescription medications (including new medications), identify any contraindications, adverse drug reactions, provide administration instructions for each medication schedule, confirm that administration instructions have been understood, and address any patient concerns regarding their medication or medication schedules.
 - Follow-up after commencing medication will be undertaken within 1-2-weeks by the disease stream nurse for assessment of early toxicity.
- Patients are provided with the contact details for the pharmacist and disease stream nurse, and can call or email if required, although they are advised of the limitations of this (i.e. business hours) and to seek alternative/urgent medical assistance if required outside of business hours.

7.9.3. Procedure of data collection with questionnaires

The questionnaires as described in section 7.7 will be completed by all participants. Completion time for all of these questionnaires is approximately 30 minutes. All questionnaire reminders will be scheduled on REDCap to be sent out on days 4 and 8 after the initial notification is sent. The REDCap reminder will automatically stop once the survey is completed. If these questionnaires are still not completed in 10 days after initial participant notification, the RC will email the participant to remind them to complete or may contact the participant and ask if they would like to complete over

the phone. This will be the final attempt by the research team to encourage participants to complete the questionnaires. Any participants who don't complete the questionnaire after the final attempt will be treated as lost follow-up.

7.10. Data analysis

Quantitative

All quantitative data will be analysed by the study statistician using STATA 17 (STATAcorp, 2021). Prior to formal data analysis, data cleaning will be performed to identify and correct for missing data and outliers, assess the distributional characteristics and summarise study measure completion rates and missing data points.

Given the relatively small sample size, and that this is a feasibility and acceptability study, analysis of outcome data will be mainly descriptive (e.g. counts/ percentages, means/ standard deviations or medians/ inter-quartile ranges, etc.). These measures will be used to summarise the information in order to describe: 1/ sample demographics; 2/ participants' acceptability and intention to use the SAMSON (performance expectancy, effort expectancy, social influence, facilitating conditions and behavioural intention), and 3/ patients' adherence, side-effect monitoring, toxicity self-management, anxiety, depression and symptoms and quality of life. Between- and within-group comparisons on the outcomes of interest will be conducted using chi-squared tests, t-tests and linear regression. Results will be used to inform the selection of appropriate endpoints and sample size calculations for a larger RCT.

Qualitative

Qualitative data, including a) answers to open questions on the healthcare professionals' and patients' experience and perception of the SAMSON intervention in the UTAUT questionnaire, b) feasibility data, and c) consultation checklists and summaries from the study nurses and pharmacists, will be summarised and analysed thematically by the RC. A thematic analysis (Liamputtong, 2020; Maguire & Delahunt, 2017) will be undertaken to identify the full range of experiences, expectations and perceptions that arose when participants discussed their experience in using the SAMSON. Thematic analysis is "a method for identifying, analysing and interpreting patterns of meanings (or themes) in qualitative data" (Braun & Clarke, 2016, p. 84). Themes are repeated patterns of meaning that are recognised in the data through categorisation and analysis of individual meaning (Houser, 2015). QSR NVivo Version 12 software (Bazeley, 2009; Bazeley & Jackson, 2013) will be used for qualitative data management. The RC will initially analyse the data. After that, a qualitative inter-rating process (Kitto et al., 2008) will be conducted by PI or another researcher, who has experience in qualitative analysis, to improve the quality of data analysis. Any disagreements will be discussed among researchers until reaching agreement. The researchers' inter-rating process helped to strengthen the credibility and trustworthiness of this study (Barbour, 2001; Mays & Pope, 2000).

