	
Primary outcomes, including:
 
 1. Acceptability (UTAUT) 2. Feasibility 
Secondary outcomes, including:
 
 1. Medication Adherence (MA) 2. Self-report adherence (ASK-12) 3. Toxicity self-management (PAM-SF) 4. Anxiety, depression and symptoms (PROMIS) 5. Quality of life (FACT-G) 6. Optimal intervention strategy 
See section 7.7 for more details on outcome assessments.
 
Data collection and results reporting will be in line with the Consolidated Standards of Reporting Trials (CONSORT) criteria for pilot RCTs (Schulz et al., 2010).

Number of participants	30-50 patients
Sample size	Sample size for this trial is pragmatic and based on both funds available and expected patient numbers in the study period.
Duration of individual's participation	16 weeks
Recruiting period	Approximately 6 months
Study duration and critical time-points	
The study will run for approximately ten months. Critical timepoints include:
 
 - Baseline (or study commencement) - Week 1 - Week 4 - Week 8 - Week 12 (intervention end) - Week 16 (endpoint assessment)
Intervention	
The intervention consists of two synergistically operating elements:
 
 - SAMSON mobile platform, including smartphone-based app to remotely prompt MA, monitor patient side-effects and deliver self-care advice; and computer-based app to enable adherence and side-effect reporting. - Health professional tele-consultations, using MI skills being trained via the MITP to promote patient's adherence and side-effect self-management by: 
 o Medication reconciliation, o MA education,

Pilot Randomized Controlled Trial Study Protocol
Version 1.0 – 2 May 2023, Amendment 1 dated 26 June 2023

	
 ○ Medication administration, missed dose and side-effect education, including side-effect management strategies, ○ Assessment of barriers and concerns ○ The structured counselling sessions will be either in person or online at baseline, week 1, 4, 8 and 12. The length of consultations will be tailored to each patient's need and adherence status, assessed by the healthcare professional who delivers the counselling sessions.

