Statistical considerations	
Quantitative data: Given the relatively small sample size, and that this is a feasibility and acceptability study, analysis of outcome data will be mainly descriptive (e.g. counts/ percentages, means/ standard deviations or medians/ inter-quartile ranges, etc.) These measures will be used to summarise the information in order to describe: 1/ sample demographics; 2/ participants’ acceptability and intention to use the SAMSON (performance expectancy, effort expectancy, social influence, facilitating conditions and behavioural intention), and 3/ patients’ adherence, side-effect monitoring, toxicity self-management, anxiety, depression and symptoms and quality of life. Between- and within-group comparisons on the outcomes of interest will be conducted, using chi squared t-tests and linear regression. Statistics and data software (STATA) version 17 (STATAcorp, 2021) will be used to analyse the quantitative data.
 
Qualitative data from the UTAUT questionnaire: will be analysed for themes in NVivo 12.
 
Results from this pilot RCT can be used to inform the design of a full RCT to evaluate the efficacy of SAMSON later.

Project timeline	
It is anticipated that the study will run for approximately 12 months. Key activities during the study timeline are:
 
January – February 2023 Protocol development Establish project team
 
March – May 2023 Acquire Peter Mac’s and Swinburne’s Ethics approvals Refine SAMSON app and MITP
 
June – November 2023 Participant recruitment
 
June 2023 – March 2024 Data collection
 
April - June 2024 Analyse data and prepare study report

Pilot Randomized Controlled Trial Study Protocol
Version 1.0 – 2 May 2023, Amendment 1 dated 26 June 2023

Study and assessment schedule

Protocol Activity	Baseline (study commencement)	Week 1	Week 4	Week 8	Week 12 (intervention end)	Week 16 (last data collection)	Will be done by
Inclusion/Exclusion criteria	x						RC (Referred by doctors/nurs/pharms)
Consent	x						Pts & RC
Demographics	x						Pts & RC
SAMSON app	x	x	x	x	x		Intervention pts & RC
Initial MI consultation: 
 Provide patient education on oral anti-cancer medicines. Identify past, present, and potential future barriers to MA. Resolve any barriers to MA, using MI techniques and document identified risks and barriers within the SAMSON web portal, for the next follow-up teleconsultation. 	x						Pharm & intervention pts

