5.1. Medication non-adherence and its burden

Medication Adherence (MA) is defined as "the extent to which a person's behaviour- taking medication, following a diet, and/or executing lifestyle changes, corresponds with agreed recommendations from a health care provider" (Sabate, 2003b, p. 3). Research has consistently shown adherence rates are typically lower among patients with chronic conditions (about 50% in developed countries and much lower in developing countries), as compared to those with acute conditions (Carter et al., 2003; Col et al., 1990; Cramer et al., 2003; Haynes et al., 2002; Sabate, 2003a; World Health Organization, 2003). Among patients with cancers, this rate varies between 16 to 100% (Bouwman et al., 2017) and often worsens overtime (Hershman et al., 2009). There is no single standard threshold for acceptable adherence, however, patients can be considered as suboptimal-adherent if their adherence rate is less than 80% (Banning, 2012; Geynisman & Wickersham, 2013; Spoelstra & Given, 2011).

Suboptimal medication adherence is often associated with poorer health outcomes and increased healthcare costs (Col et al., 1990; Kane & Shaya, 2008). Studies have shown that poor adherence to prescribed regimens can significantly impact survival rates (Makubate et al., 2013), and result in patients' disease progression, reduced functional ability, increased risk of hospitalisation, and lower quality of life (Col et al., 1990; Fuso et al., 1995; Garcia-Aymerich et al., 2000). Annually, in Australia, it is estimated that 250,000 Australians experience medication-related hospital admissions, which costs Australian taxpayers \$1.4 billion (Lim et al., 2019). MA and error management are essential for tackling chronic conditions effectively and play critical roles in improving healthcare today (Sabate, 2003a).

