5.3. SAMSON intervention solution

Harnessing the potential of technologies, we developed SAMSON - a novel patient-centred, comprehensive digital solution to improve MA in cancer. The solution comprises two components:

Pilot Randomized Controlled Trial Study Protocol
Version 1.0 – 2 May 2023, Amendment 1 dated 26 June 2023

- 1) SAMSON mobile app involving individually tailored smartphone alerts and real-time advice for side-effect self-management. The beta-version of SAMSON mobile app was tested by 30 people with haematological cancer at Peter Mac in 2021 (HREC/74134/PMCC).
- 2) Health professional tele-consultations, using MI skills being trained via the MITP to promote patient's adherence and side-effect self-management. The MITP is a digital training platform, which was created to provide general training on motivational interviewing, communication skills with focus on medication adherence aspects for oncology clinicians. The MITP was co-designed with healthcare professionals, stakeholders and consumer representatives, and developed in 2022. It is available on Peter Mac's learning management system and being tested by healthcare professionals at the hospital. The data collection is expected to complete in March 2023 the latest.

Pilot Randomized Controlled Trial Study Protocol
Version 1.0 – 2 May 2023, Amendment 1 dated 26 June 2023

6 Objectives

The objective of this work is to evaluate the acceptability, feasibility (recruitment, randomisation, retention, intervention adherence and assessment processes) and potential efficacy of the SAMSON intervention solution among 30 to 50 patients with haematological, lung or melanoma cancer newly administered oral anti-cancer medicines.

7 Methods

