7.2. Number of participants and study duration

Thirty to fifty patients will be recruited into the pilot RCT. The study will run for 16 weeks. During this 16-week, the patient in the intervention arm will:

- have access to the SAMSON mobile app (the first component of the intervention solution) throughout the study period, and
- receive initial pharmacist consultation and tele-consultations provided by their care team at Peter Mac, i.e nurses or pharmacists, in weeks 1, 4, 8 and 12.

All randomisations will be done by the study statistician.

Recruitment will be undertaken over a period of 6 months and the intervention is expected to be completed in ten months from recruitment commencement.

The patient in the controlled arm will receive usual care at the hospital (see details in section 7.9.2).

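### Section 7.10 plans both between-arm and within-arm tests without saying that potential efficacy rests on the between-arm difference; a within-arm test cannot separate SAMSON from a shared time trend.

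*Protocol*

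**What the plan says.** The protocol's objective (synopsis and section 6) covers acceptability, feasibility and the "potential efficacy of the SAMSON intervention solution among 30 to 50 patients". The design is a 1:1 randomised comparison with usual care. Section 7.2 gives the size: "Thirty to fifty patients will be recruited into the pilot RCT". The synopsis gives its basis: "Sample size for this trial is pragmatic and based on both funds available and expected patient numbers in the study period".

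Section 7.10 says that "analysis of outcome data will be mainly descriptive" and then commits to named tests: "Between- and within-group comparisons on the outcomes of interest will be conducted using chi-squared tests, t-tests and linear regression". The synopsis (Statistical considerations) has nearly the same sentence: "Between- and within-group comparisons on the outcomes of interest will be conducted, using chi squared t-tests and linear regression". On use, section 7.10 adds: "Results will be used to inform the selection of appropriate endpoints and sample size calculations for a larger RCT".

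ASK-12, PAM-SF, PROMIS and FACT-G are each collected twice, the second time at week 12. Medication refill adherence (MRA) is assessed once, at week 16 (section 7.7.2.1). Neither place that describes the analysis says which comparison carries the potential-efficacy objective, or what the within-group tests are for.

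**The concern.** A test within one arm has as its null hypothesis that scores in that arm do not change between the two questionnaires. The question of interest is whether SAMSON differs from usual care. The two separate whenever scores move for reasons unrelated to SAMSON, and the protocol gives grounds to expect that they will. It says of adherence in cancer that it "often worsens overtime" (section 5.1). Participants are about to start, or are less than 12 months into, oral anti-cancer medicine (section 7.6.1). Usual care itself includes pharmacist and clinician education and early nurse follow-up (section 7.9.2), so the control arm may move as well.

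A significant change in the SAMSON arm, or significance there but not in control, is easily taken for a signal when the arms do not differ. In the other direction, if scores tend to worsen and SAMSON holds them steady, the within-arm test shows nothing although the arms do differ. Either reading could affect which scales are chosen for the full trial.

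**Working it through.** The protocol gives no alpha, effect size or SD and no power calculation, so there is no planned figure to reproduce. The check asks how often a within-arm test rejects when SAMSON does nothing.

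**Inputs from the protocol.** 30 to 50 patients allocated 1:1, so 15 to 25 per arm; two measurements for each of the four questionnaires.

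**Assumptions, not in the protocol.** Two-sided 5% tests; normal scores with SD 1 at both times; the same shift δ of 0.2, 0.3 or 0.5 SD in both arms; correlation r of 0.5 or 0.7 between the two scores; no dropout; zero treatment effect.

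**Step 1: within-arm paired t-test.** The SD of the change is √(2(1−r)), which is 1.000 at r=0.5 and 0.775 at r=0.7. The standardised change is d = δ/√(2(1−r)). Rejection follows a noncentral t distribution with n−1 degrees of freedom and noncentrality d√n. For example, n=25, r=0.7 and δ=0.5 give d = 0.5/0.775 = 0.645 and noncentrality 0.645×5 = 3.23 against a critical value of 2.064, hence 87%.

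| n per arm | r | δ=0.2 | δ=0.3 | δ=0.5 |
|---|---|---|---|---|
| 15 | 0.5 | 11% | 19% | 44% |
| 15 | 0.7 | 15% | 29% | 64% |
| 25 | 0.5 | 16% | 30% | 67% |
| 25 | 0.7 | 24% | 46% | 87% |

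The test is symmetric, so the same percentages apply to a shared improvement and to a shared deterioration. Only the direction of the significant result changes.

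**Step 2: significant in SAMSON but not in control.** The arms are independent and share the same rejection probability p, so this pattern has probability p(1−p). Across the table it runs from 0.11×0.89 ≈ 10% to about 25% (at p=0.46, 0.46×0.54 ≈ 0.25).

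**Step 3: between-arm tests.** In 20,000 simulated trials per setting, with common shifts of 0, 0.3 and 0.5 SD, the t-test on change and the regression of the week-12 score on arm and first score rejected in 4.6% to 5.1%. A shared trend cancels in the contrast.

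**Step 4: precision from adjustment, 25 per arm.** For an unadjusted week-12 t-test the 95% CI half-width is t(0.975, 48)×√(2/25) = 2.011×0.283 = 0.57 SD. Adjusting for the first score multiplies it by about √(1−r²): 0.57×0.866 = 0.49 SD at r=0.5, and 0.57×0.714 = 0.41 SD at r=0.7.

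**Step 5: is the first score taken before the intervention?** Section 7.1 has baseline questionnaires completed before randomisation, and section 7.5 has the four questionnaires completed before the participant is told the arm. The synopsis, the assessment schedule and section 7.7.2 place the same questionnaires at week 1, and the schedule leaves their baseline column empty. The schedule also starts the app and the initial consultation at baseline. On that reading the first score could already reflect the intervention, and adjusting for it could remove part of the effect.

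**The case against.** The randomised contrast is planned and is named first in the sentence. The analysis is mainly descriptive, and the primary outcomes are acceptability and feasibility. Nothing says that a within-arm p-value will support efficacy. The feasibility judgement for the full trial rests on the thresholds in Table 1, none of which is an efficacy result. All of this stands. A reader might infer that the plan discards the control arm, or that it treats a within-arm p-value as evidence of efficacy. The document supports neither.

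Direction matters too. The only trend that the protocol cites is worsening adherence, and it documents none for PAM-SF, PROMIS or FACT-G. A favourable shared shift is therefore an assumption, and the percentages should not be read as the chance of a false claim of benefit. Regression to the mean is also unsupported, because entry does not select on any of these scores.

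The precise regression model may properly sit in a statistical analysis plan, so its absence is no defect; it appears here only as part of the remedy. Within-arm means, SDs and correlations are useful for planning the next trial, which argues for reporting them but not for testing them.

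The objection does not reach the tests themselves. Describing the analysis as mainly descriptive does not withdraw tests that the same section commits to, and section 7.10 gives their results a stated route into the design of the full trial.

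**Conclusion.** The point holds as a gap in what the plan states. Two kinds of test are planned for the outcomes that bear on potential efficacy, and the protocol does not say that only the between-arm one speaks to it. For the four questionnaires, the within-arm test rejects with no SAMSON effect in 11% to 64% of cases at 15 per arm and 16% to 87% at 25, in whichever direction the trend runs, against about 5% between arms. These figures rest on the assumed common shift, correlation and test level. With no shift the within-arm test would reject at its nominal 5%.

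MRA has a single time point, so the within-arm problem does not arise there. The consequence is a risk of misreading in either direction, modest for a pilot of this kind. It is worth correcting because the results inform the choice of endpoints and the size of the full trial, and because the change costs almost nothing.

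**What to change.** In section 7.10 and in the synopsis (Statistical considerations):

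- Replace the within-group tests with descriptive within-arm change: mean and SD, no p-values.
- State that potential efficacy is judged only on the between-arm difference with its 95% CI.
- For ASK-12, PAM-SF, PROMIS and FACT-G, estimate that difference by linear regression of the week-12 score on arm and the first-questionnaire score. For MRA, report the between-arm difference at week 16.
- Before fixing that model, reconcile sections 7.1 and 7.5 with the synopsis, the schedule and section 7.7.2 on when the first questionnaire is completed, so that the covariate is measured before the intervention.

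The cost is a sentence or two in two places and one clarification of timing. No new data are needed, and linear regression is already planned. The downside is that within-arm p-values can no longer be reported.
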